## 8 ANALYSIS POPULATIONS

### 8.1 Full Analysis Set

The Full Analysis Set (FAS) will consist of all randomized subjects who receive at least 1 dose of study drug and have at least 1 post-baseline efficacy assessment. All subjects in the FAS will be analyzed based on their randomized treatment group, regardless of the treatment they actually received. The FAS population will be the primary analysis population. All efficacy analyses will be performed on the FAS.

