## **8.3 Safety Analysis Set**

The Safety Analysis Set (SAS) will include all randomized subjects who receive at least 1 dose of study drug. All subjects in the SAS will be analyzed based on the treatment group they actually received. All safety analyses will be conducted on the SAS.

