### 9.5 Handling of Missing Data

Missing values at baseline will not be imputed in any situation. For efficacy analyses, values missing post-randomization will be imputed using LOCF (unless otherwise specified); only post-randomization values on treatment will be used for imputation. For safety analyses, observed cases will be used.

Imputation will not be conducted for AEs missing severity or relationship to study medication. AEs missing severity will be excluded from summaries of AEs by severity. AEs missing relationship will be excluded from summaries of related AEs.

For AE start date, if only month and year are present, and they are the same month and year as the treatment start date, the day will be imputed by the treatment start day (and the AE will be considered treatment-emergent).

Rules for partial and missing dates for prior and concomitant medications are given in [Appendix 2](#).

Drug interruptions with partial start and/or stop dates will be assumed to be 1 day in length, and will be assumed to have occurred in the visit interval prior to when the interruption was collected (eg, if a drug interruption with partial dates was collected at the Week 10 visit, it is assumed that the interruption occurred between the previous visit [eg, Week 6] and the Week 10 visit).

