**Table 2. Visit Windows for Assessments Done at Day 1, Weeks 2, 6, 10, and 12**

Visit	Target Study Day	Visit Window
Week 2/Visit T2	15	2, 29
Week 6/Visit T3	43	30, 57
Week 10/Visit T4	71	58, 78
Week 12/Visit T5	85	> 78

For parameters not measured at Week 2/Visit T2 and Week 10/Visit T4, the Visit Window for Week 6/Visit T3 is (2, 64) while Week 12/Visit T5 is > 64. For parameters not measured at Week 2/Visit T2 and Week 6/Visit T3, the Visit Windows for Week 10/Visit T4 and Week 12/Visit T5 are (2, 78) and > 78, respectively.

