## 11.2 Sensitivity Analysis

A sensitivity analysis of the primary LOCF analysis will be performed using the same ranked ANCOVA as the primary analysis, only for this analysis, all subjects from the FAS who discontinued early will be assigned the lowest available rank. All such subjects will be assigned the same value and thus the same rank will be assigned (i.e., treating each subject as a tie). The ranked ANCOVA will then be performed on this dataset. An estimate of the placebo-corrected median difference will not be provided for this analysis.

An additional sensitivity analysis will be conducted by repeating the primary analysis on the PPS population.

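### The assigned-rank sensitivity analysis (SAP 11.2) is confined to the FAS, so it omits dosed subjects who have no post-baseline efficacy assessment

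*SAP*

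**What the plan says.** SAP 11.2 plans two sensitivity analyses of the primary endpoint. In the first, "all subjects from the FAS who discontinued early will be assigned the lowest available rank"; these subjects are tied with one another and the ranked ANCOVA is refitted. The second is on the Per Protocol Set: "An additional sensitivity analysis will be conducted by repeating the primary analysis on the PPS population". Under SAP 8.2 the PPS is drawn from FAS subjects who completed treatment.

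SAP 8.1 (and protocol 9.2.1) defines the FAS as "all randomized subjects who receive at least 1 dose of study drug and have at least 1 post-baseline efficacy assessment", and adds: "All efficacy analyses will be performed on the FAS".

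The only defined set without the post-baseline condition is the safety set in SAP 8.3: "The Safety Analysis Set (SAS) will include all randomized subjects who receive at least 1 dose of study drug". It is used for safety only and is analysed by treatment received.

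For LOCF, SAP 9.5 says that "only post-randomization values on treatment will be used for imputation". This explains why the primary analysis cannot use a subject with no post-baseline value. It does not govern an assigned rank.

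The first scheduled post-baseline TG is at Week 2, Day 15 ± 3 (protocol 6.4.2). The ET visit also includes a fasting lipid panel (protocol 6.6). SAP 9.8 assigns ET visits to analysis windows, and the Week 2 window opens on Day 2 (SAP Table 2). Efficacy visits more than 2 days after the last dose are not considered.

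**The concern.** The first analysis in 11.2 is there to show whether the primary result depends on how dropouts are handled. LOCF needs a value to carry forward, so the primary analysis has to leave out a subject who has none. The assigned-rank analysis has no such need. Its outcome is set by rule, and the other model terms (treatment, statin and ranked baseline TG) are known before the first dose. Restricting it to the FAS carries over the one limitation of the primary analysis that it could remove.

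At stake is the meaning of a reassuring result. If dosed subjects without a post-baseline assessment were more common in one arm, 11.2 would not show what happens when they are counted. With about 30 per arm, one or two subjects tied at an extreme rank carry visible weight.

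**Working it through.** **1. The plan's own figure.** SAP 9.1: difference 35, SD 43, two-sided alpha 0.05, power 80%, dropout 15%.

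- Normal approximation: n = 2 × (1.960 + 0.842)² × 43² / 35² = 2 × 7.85 × 1849 / 1225 ≈ 23.7, so 24 evaluable per arm; 24 / 0.85 = 28.2, so 29 randomized.
- Exact t-test: 25 evaluable per arm (power 0.805); 25 / 0.85 = 29.4, so 30 randomized.

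The stated 30 per arm is reproduced. This point does not change it.

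**2. Who is left out.** Expected dropouts are 0.15 × 90 = 13.5, or 4.5 per arm, and protocol 4.3 says they are not replaced. Three cases arise before Week 2:

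- ET lipid sample within 2 days of last dose: the value falls in the Week 2 window, so the subject is in the FAS and in 11.2.
- ET sample more than 2 days after last dose: the value is not used for efficacy. The SAP does not say whether it still confers FAS membership.
- No Week 2 and no ET sample: the subject is outside the FAS, hence outside the primary, the secondary and both sensitivity analyses.

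The documents give no number for the second and third cases. It can be anything from 0 to about 13.

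**3. Leverage, two arms.** Assumptions: 30 randomized per arm; 5 active and 4 placebo dropouts, all tied at the unfavourable end; other percent changes normal with difference 35 and SD 43; rank test at 0.05. The rejection rate here measures leverage. A higher rate is not better, because this analysis is a stress test.

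| Dropouts excluded by the FAS condition | Rejection rate |
|---|---|
| None (all dosed subjects kept) | about 47% |
| 1 active, 1 placebo | about 53% |
| 1 active, 0 placebo | about 59% |
| 2 active, 0 placebo | about 74% |

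**4. Leverage, the SAP's three-arm model.** Ranked ANCOVA with treatment, statin and ranked baseline TG; 2,000 trials per cell; lognormal baseline (median 700 mg/dL, log-SD 0.3, assumed); 300 mg against placebo. Dropouts are listed as placebo/300/600.

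| Dropouts excluded | Dropouts 4/5/5 | Dropouts 2/6/5 |
|---|---|---|
| None | 0.46 | 0.19 |
| 1 in every arm | 0.50 | 0.24 |
| 1 per active arm only | 0.58 | 0.30 |
| 2 per active arm only | 0.72 | 0.44 |
| 3 per active arm only | 0.81 | 0.58 |
| 4 per active arm only | 0.88 | 0.71 |

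Balanced exclusion moves the result by 4 to 5 points. Exclusion from the active arms only moves it by 10 points or more, in favour of gemcabene.

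**5. Direction.** SAP 11.2 does not say which end of the ranking is meant. With percent change ranked in ascending order, the lowest rank is the largest TG fall. Dropouts would then sit at the favourable end, and the sign of the effect reverses: in the two-arm setting, excluding 2 active-arm subjects lowers rejection from about 71% to about 55%. Who is left out does not change.

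**The case against.** The strongest defence is that 11.2 is presented as a sensitivity analysis of the LOCF analysis. Keeping the same set isolates the imputation rule and obeys the SAP's own statement that efficacy is analysed on the FAS. That is right as far as it goes: the documents do not contradict themselves, and this is a limitation rather than an error. It does not remove the gap, since no other planned analysis covers these subjects.

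Several stronger readings are tempting, and the documents do not support them:

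- *Everyone who stops before Week 2 is lost.* Protocol 4.3 asks staff to make every effort to complete the ET visit, and a timely ET lipid panel brings the subject into the FAS.
- *A known share of the 13 to 14 expected dropouts is affected.* The documents give no such share.
- *Very early stops reflect intolerance and will differ by arm.* Protocol 1.4 describes gemcabene as generally well tolerated. An imbalance is possible, but nothing in the documents predicts it.
- *Power falls from about 82%.* That starting point has nobody at the assigned rank. In 11.2 every FAS subject who discontinued early is already there, so the reference is about 47%.
- *The loss would be hidden.* SAP 10.1 tabulates disposition by randomized arm for all randomized subjects, the FAS and the safety set, so the number outside the FAS follows largely by subtraction. A count shows the loss but does not test the result against it.

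**Conclusion.** The point holds as one about the analysis set. Dosed subjects who miss both Week 2 and a usable ET lipid sample are in no planned primary, secondary or sensitivity efficacy analysis, although the assigned-rank model could include them. If there are none, the two versions of 11.2 are identical. If they are few and balanced, the effect is modest: about 47% against 53% in the two-arm check. If they fall in the active arm only, it is material: about 59% with one and 74% with two.

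These figures rest on the design difference and SD, on normal data, on dropout near the plan, and on dropouts being placed at the unfavourable end. The split between arms is assumed, so the figures illustrate leverage and do not predict this trial's result. This is a supportive analysis in a Phase 2 trial and the primary is not affected. The change is worth making because it is cheap and removes a possible bias.

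**What to change.** In SAP 11.2, define the assigned-rank analysis on all randomized subjects who took at least one dose and have a baseline TG, analysed as randomized. Assign the unfavourable outcome to every early discontinuation, including those with no post-baseline TG, and state which end of the ranking that is. Add the matching exception to the FAS rule in SAP 8.1. Report by arm how many dosed subjects have no post-baseline TG. Make the change before the unblinding that SAP 4.1 starts once the last subject completes Week 12.

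The cost is a phrase in 11.2, a line in 8.1 and one count per arm. No new data are needed, and the sample size and the primary FAS analysis stay as they are. The downside is that the sensitivity result may look less favourable.

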## 11.3 Secondary Analysis

Secondary analyses will be conducted using the methodology detailed below. All secondary analyses will be conducted using the FAS population (or the specific subgroup within the FAS population, eg, diabetic subjects).

The secondary endpoints are as follows:

- CFBL and percent CFBL to Weeks 2, 6, 10, 12, and EOS in fasting serum TG;
- CFBL and percent CFBL to Weeks 2, 6, 10, 12, and EOS in TC, non-HDL-C, HDL-C, and VLDL-C;
- CFBL and percent CFBL to Weeks 10, 12, and EOS in LDL-C LDL-TG, VLDL-TG, HDL-TG;
- CFBL and percent CFBL to Weeks 10, 12, and EOS in Apo B, ApoA-I, ApoA-II, ApoC-II, ApoC-III, and ApoE;
- CFBL and percent CFBL to Week 12 in lipoprotein size and particle number (NMR);
- CFBL and percent CFBL to Weeks 10, 12, and EOS in hsCRP, IL-6, SAA, adiponectin, and fibrinogen; and
- Percent of subjects achieving a TG value < 500 mg/dL (5.65 mmol/L) at Weeks 10, 12, and EOS.

Continuous secondary efficacy endpoints that measure CFBL and percent CFBL will be analyzed using ranked ANCOVA with CFBL or percent CFBL in the respective parameter as the dependent variable; treatment, baseline statin (yes or no) and qualifying TG stratum ( $> 880$  mg/dL or  $\leq 880$  mg/dL) as factors; and the respective ranked baseline as a covariate. Qualifying TG stratum will not be included as a factor in secondary ANCOVA models where TG is the parameter of interest (dependent variable). For the EOS time point, EOS is defined in [Section 9.4](#) or all other time points, missing values will be imputed using LOCF, with the last on-treatment value carried forward to that time point.

Secondary efficacy endpoints that are continuous will be analyzed using ranked ANCOVA and secondary efficacy endpoints that are binary will be analyzed using logistic regression.

The output from each ranked ANCOVA will be consistent with the primary efficacy model.

The percent of subjects achieving a TG value < 500 mg/dL (5.65 mmol/L) at Weeks 10, 12, and EOS will be analyzed using a logistic regression with treatment, baseline statin use (yes or no), and baseline TG value as independent factors. The percent of subjects in each treatment group achieving a TG value < 500 mg/dL, and the odds ratios (ORs) with 95% confidence intervals and p-values will be presented to compare gemcabene 300 mg and gemcabene 600 mg separately with the placebo group.

The SAS code used to conduct a logistic regression model is provided below:

```
proc logistic data=data;
  class TRT(ref="Placebo") Statin;
  model Outcome(event="event")= TRT Statin Base / expb;
run;
```

Descriptive statistics for all secondary efficacy parameters will also be provided by visit.

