**Screening Period:** All potential subjects will participate in the Screening Period, including Screening Visit 1 (S1), Screening Visit 2 (S2) and, if necessary as outlined below, optional Screening Visit 3 (S3) up to 28 days prior to Study Day 1 (Visit T1). For potential subjects on stable statin therapy and/or ezetimibe for  $\geq 12$  weeks who do not require a wash-out period, S1 will be their first study visit. For other subjects who have been washing out their other lipid medications, S1 occurs after the full required washout has been completed.

During this Screening Period, potential subjects must meet the TG qualifying values in order to be eligible for randomization on Day 1 (Visit T1).

At the end of this 2-4-week diet and lifestyle stabilization and TG qualifying period, eligible subjects must have an average fasting TG level  $\geq 500$  mg/dL to  $< 1500$  mg/dL in order to qualify for the 12-week double-blind treatment period. The TG level for qualification will be based on the average (arithmetic mean) of the Visit S1 and Visit S2 values. If a subject's average TG level from Visit S1 and Visit S2 falls outside the required range for entry into the study, one additional sample for fasting TG value can be collected 1 week later (at the Optional Visit S3), and the arithmetic mean from Visits S2 and S3 will then be used to determine eligibility.

**Double-Blind Treatment Period:** Eligible subjects will be randomized on Day 1 via an interactive web/voice response system (IWRS/IVRS) on Study Day 1 in a 1:1:1 ratio (30 subjects per group) to one of the following treatment groups:

- Gemcabene 300 mg QD, or
- Gemcabene 600 mg QD, or
- Placebo

Subjects will be stratified by baseline statin therapy (yes or no) and qualifying TG value ( $< 880$  mg/dL or  $\geq 880$  mg/dL) to ensure background therapies and baseline TG values are balanced across all treatment groups.

The Follow-up Visit will occur 4 weeks ( $\pm 3$  days) after the last dose of study drug.

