# **9 OVERALL STATISTICAL CONSIDERATIONS**

## **9.1 Sample Size Computation**

Approximately 90 subjects (30 subjects per treatment group) will be randomized into 1 of 3 treatment groups: gemcabene 300 mg, gemcabene 600 mg or placebo.

A sample size of 30 randomized subjects in the gemcabene 300 mg group, 30 randomized subjects in the 600 mg group and 30 randomized subjects in the placebo group is expected to provide 80% power to detect a difference of 35% in the percent change in TG from baseline to EOS between either of the gemcabene treatment groups and the placebo group. This calculation is based on a 2-sided t-test at the 5% level of significance ( $\alpha = 0.05$ ), a common standard deviation (SD) of 43, and a drop-out rate of 15%.

In this Phase 2 study, both the gemcabene 300 mg and the 600 mg treatment groups will be compared to placebo separately using a 5% significance level ( $\alpha = 0.05$ ). No statistical adjustment will be used for these two comparisons of the primary efficacy endpoint.

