### 9.3 Baseline Definitions

Baseline for a given parameter is generally defined as the last assessment prior to the first dose of the study drug but varies depending on the parameter:

- Baseline for TG is defined as the average of the (Screening Visits ([S1 and S2] or [S2 and S3] occurring up to 28 days prior to Study Day 1) and Study Day 1 [pre-dose]) values. For subjects not requiring screening visit S3, the average of Screening Visits 1 and 2 and Study Day 1 (pre-dose), with each given equal weight, will be used. For subjects requiring screening visit S3, the average of Screening Visits 2 and 3 and Study Day 1 (pre-dose), with each given equal weight, will be used. If one of the screening visits is not completed and data were collected at a subsequent unscheduled visit, data from this visit will be used in the baseline calculation in place of the planned screening visit.
- Baseline for TC, non-HDL-C, HDL-C and VLDL-C is defined as the average of the last two pre-dose values (generally will be the average of Visit S2 and pre-dose Study Day 1/Visit T1). If one of the values that contribute to baseline (eg, the value from the Screening/Visit S1) is missing, the non-missing value will be used for baseline.
- Baseline for apolipoproteins (ie, Apo B, ApoA-I, ApoA-II, ApoC-II, ApoC-III, and ApoE), LDL-C (ultracentrifugation), LDL-TG, VLDL-TG, HDL-TG, hsCRP, IL-6, SAA, adiponectin, fibrinogen, ANGPTL4, fasting insulin levels, FPG, and HbA1c is defined as the value from pre-dose Study Day 1/Visit T1. If the value is missing on Day 1, the last non-missing value prior to first dose will be used.
- Baseline for ECGs, vital signs, visceral adiposity measures (BMI, waist circumference, weight), and safety laboratory parameters (ie, chemistry, hematology, coagulation, and urinalysis parameters) is defined as the last pre-dose measurement (pre-dose Study Day 1/Visit T1 or prior) for the corresponding parameter.

Note that subjects have to be in a fasting state during an unscheduled visit in order for the unscheduled visit assessments to be considered for baseline calculations.

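### The TG <500 mg/dL percentages count carried-forward early values, and a few subjects already below 500 at baseline, as achieving the goal

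*SAP*

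**What the plan says.** SAP 11.3 defines the endpoint as the percent of subjects with TG below 500 mg/dL, which "at Weeks 10, 12, and EOS will be analyzed using a logistic regression with treatment, baseline statin use" and baseline TG as independent factors. The population is the FAS (SAP 8.1): at least one dose and one post-baseline efficacy assessment. Arm percentages are presented with odds ratios against placebo.

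Three other rules decide who counts as achieving.

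- Entry, SAP 7.1: "The TG level for qualification will be based on the average (arithmetic mean) of the Visit S1 and Visit S2 values". That mean must be at least 500 and below 1500 mg/dL; otherwise S2 and S3 may be used. Day 1 TG plays no part in eligibility.
- Baseline, SAP 9.3: for subjects without an S3 visit, "the average of Screening Visits 1 and 2 and Study Day 1 (pre-dose), with each given equal weight, will be used". With an S3 visit it is S2, S3 and Day 1.
- Missing data, SAP 9.5: "For efficacy analyses, values missing post-randomization will be imputed using LOCF", unless another rule is given, using on-treatment values only. No other rule is given for this endpoint. The EOS definition in SAP 9.4 is worded for continuous parameters.

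The early-discontinuation sensitivity analysis in SAP 11.2 covers the primary endpoint only. SAP 4.3 drops the per-protocol repeat of the secondary analyses.

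**The concern.** The indication in Protocol 3.2 is framed around bringing TG below 500 mg/dL, and this endpoint measures that directly. A reader will take an arm's percentage to mean subjects who came down to the goal and were there on treatment at the end. Two kinds of subject do not fit that meaning.

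The first stopped early with a last on-treatment TG below 500. LOCF scores this subject as at goal at later visits that were never attended. The second had a three-visit baseline already below 500 and counts as achieving if still below 500 later. Both push the percentages up. Adjusting the logistic model for baseline TG does not change the reported percentages, and no planned analysis shows how much of each percentage comes from either source.

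**Working it through.** **The plan's own figure.** SAP 9.1 says 30 per arm will "provide 80% power to detect a difference of 35% in the percent change in TG from baseline to EOS". "This calculation is based on a 2-sided t-test at the 5% level of significance", with "a common standard deviation (SD) of 43, and a drop-out rate of 15" percent. The normal approximation is n = 2 × (1.960 + 0.842)² × 43² / 35² = 23.7, so 24 per arm. The exact t-test needs 25 (power 80.5%). 25 / 0.85 = 29.4, rounded up to 30. The stated size is reproduced. The dropout figure used below is therefore 0.15 × 30 = 4.5 subjects per arm. The documents give no expected rate or power for the TG <500 endpoint.

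**LOCF.** Let p be the goal rate among subjects with Week 10/12 data, and f the share of dropouts whose last on-treatment TG was below 500. Assume all 15% are in the FAS and have no Week 10 or Week 12 value.

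- LOCF: 0.85p + 0.15f
- Dropouts counted as not achieving: 0.85p
- Excess: 0.15f, whatever p is

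For f = 0.2, 0.5 and 0.8 the excess is 3.0, 7.5 and 12.0 points. The ceiling, f = 1, is 15 points (4.5 of 30). The documents do not give f.

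**When baseline falls below 500.** With qualifying mean M and Day 1 value D, baseline is (2M + D)/3. It is below 500 exactly when D < 1500 − 2M: D below 500 at M = 500, below 450 at M = 525, below 400 at M = 550, below 300 at M = 600. Example: M = 510 and D = 430 give 1450/3 = 483.

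**How often, and how much it matters.** The entry rules were simulated: S1 of 425 to below 1800 (Protocol 6.3.1), qualifying mean of 500 to below 1500, higher value at most 1.5 times the lower (Protocol 4.1), and the S3 path. TG was assumed lognormal with population median 450–700 mg/dL, between-subject log-SD 0.35–0.5 and within-subject CV 15–30%. None of these inputs is in the documents. EOS was the mean of two later draws, unchanged or reduced by 30% or 50%. Goal rates below are for all subjects, then for those with baseline at least 500.

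| Median, log-SD, CV | Baseline <500 | No effect | 30% reduction | 50% reduction |
|---|---|---|---|---|
| 700, 0.35, 15% | 2.1% | 5.7 / 4.6 | 43.0 / 41.8 | 81.5 / 81.1 |
| 600, 0.40, 20% | 3.9% | 10.3 / 8.5 | 49.8 / 47.8 | 84.2 / 83.6 |
| 450, 0.50, 30% | 7.3% | 18.7 / 15.5 | 54.7 / 51.6 | 84.4 / 83.2 |
| 450, 0.35, 30% | 10.3% | 25.9 / 22.0 | 68.2 / 65.2 | 93.2 / 92.4 |

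Across all settings, 2–10% had baseline below 500 (about 0.6 to 3 of 30 per arm). Restricting to baseline at least 500 lowered the rate by about 0.3 to 4 points.

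**The treatment comparison.** In the second row, the drug-minus-placebo difference at a 30% reduction is 49.8 − 10.3 = 39.5 points for all and 47.8 − 8.5 = 39.3 restricted. At a 50% reduction it is 73.9 and 75.1. In the last row at 50% it is 67.3 and 70.4. Across all settings the restriction moved the difference by about −0.4 to +3.4 points. For LOCF with equal 15% dropout, the difference shifts by 0.15 × (f on drug − f on placebo); f of 0.5 against 0.2 would give 4.5 points.

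**The case against.** TG below 500 at EOS can fairly be read as a status measure, and the protocol prespecifies it in the FAS with the same model. Requiring baseline at least 500 in the main analysis would substitute a different endpoint. This stands, and is a reason to keep the FAS denominator.

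Whether LOCF overstates depends on the target. It also scores a dropout last seen at or above 500 as a failure. If the target were the result had dropouts stayed on drug, the error could go either way. This stands too: the upward direction holds only relative to being at goal on treatment at Week 10/12.

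The documents also narrow the LOCF count. An on-treatment early-termination value on Days 58–78 is an observed Week 10 value (SAP 9.8), values more than 2 days after last dose are not used, and dropouts with no post-baseline assessment are outside the FAS. A reader might infer that 4 to 5 subjects per arm are wrongly counted. That is a ceiling, needing every planned dropout to lack Week 10/12 data and to end below 500.

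Two other strong readings are tempting. One is that up to a quarter of achievers were at goal from the start. In the simulation that share was about 15–26% only with no drug effect, and about 3–14% with a 30% or 50% reduction. Nor do such subjects count automatically: with no drug effect, only 45–62% of them were below 500 at EOS. The other is that these subjects dilute the contrast with placebo. Randomization and the baseline covariate largely protect it, and the simulated shift was small and of mixed sign at a 30% reduction.

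Finally, SAP 9.2 treats secondary p-values as descriptive, so no error rate is at stake.

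**Conclusion.** The point holds for the reported arm percentages, in a limited form. Both counting routes follow from the SAP's general rules rather than from an explicit statement about this endpoint. Relative to being at goal on treatment at Week 10/12 after starting at 500 or above, LOCF raises an arm's percentage by 0.15 × f at the planned dropout (3–12 points for f of 0.2–0.8, ceiling 15). Baselines below 500 raise it by about 0.3–4 points. The two can overlap, so they should not simply be added. The first figure rests on an assumed f, the second on assumed TG distributions and within-subject variability.

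The odds ratios are largely protected from the baseline issue. LOCF would bias the comparison only if dropout or early response differs between arms, which the documents do not let one judge. The primary analysis, sample size and error rates are unaffected. This is a cheap improvement to one secondary endpoint, not a flaw in the trial's main conclusion.

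**What to change.** In SAP 11.3:

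- Count FAS subjects with no on-treatment TG at Week 10 or Week 12 as not achieving at that visit, and as not achieving at EOS if both are missing. If only one is missing, EOS uses the other, as now. This also settles EOS for the binary endpoint.
- Keep the LOCF version as a supportive analysis.
- Keep the FAS denominator, and add a supportive analysis restricted to baseline TG of at least 500 mg/dL. The restriction uses pre-dose data only, so the comparison stays randomized.
- Report by arm the number with baseline below 500 and the number of carried-forward results.

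The cost is a few sentences, slightly lower percentages and one extra table. No new data are needed.
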